# **Appendix 2 ECOG/WHO Performance Status Assessment**

Two observers will be required to assess performance status. If there is any discrepancy between the two scores, the highest (worst) assessment will be used

Grade	
0	Asymptomatic (Fully active, able to carry on all pre-disease activities without restriction)
1	Symptomatic but completely ambulatory (Restricted in physically strenuous activity but ambulatory and able to carry out work of a light or sedentary nature. For example, light housework, office work)
2	Symptomatic, <50% in bed during the day (Ambulatory and capable of all self care but unable to carry out any work activities. Up and about more than 50% of waking hours)
3	Symptomatic, >50% in bed, but not bedbound (Capable of only limited self-care, confined to bed or chair 50% or more of waking hours)
4	Bedbound (Completely disabled. Cannot carry on any self-care. Totally confined to bed or chair)
5	Death

Page 97 of 98

#### Appendix 3 **Summary of Protocol Amendments**

#### **Protocol Amendment 1**

This protocol amendment, dated 16 December 2019, addressed the following changes to the study protocol (Final version 1.0, 9 April 2018):

- Removal of the exclusion criterion that limits the number of treatment regimes allowed prior to anti-PD-1 therapy to one, for patients enrolling in Cohort B of the study.
- Amendment of the inclusion criterion that specifies the number of doses of prior treatment with anti-PD-1 therapy that are required for Cohort B of the study.
- Amendment of dosing schedule of nivolumab to accommodate an investigator choice between 3mg/kg 2 weekly, 240 mg 2 weekly or 480mg 4 weekly.
- Change of time between end of other investigational product and first study dose from 4 weeks to 3 weeks
- Clarification that the biopsy sample used for PD-L1 testing at Screening is the same as that used for immunological marker testing for Cohort A of the study.
- Confirmation that study assessments, as well as blood samples, may be taken the day before a scheduled dosing day.
- Inclusion of final data from the IMM-101-008 study.
- Clarification that an end of study visit should be carried out, if possible, following completion or early termination. Should this not be possible, unresolved adverse events should still be followed up.
- Clarification of assessment of response.
- Addition of more sites.
- Clarification of disease control rate.
- Clarification of sub-groups for analysis.
- Correction of error in survival rates quoted.
- Correction to Investigator Statement.
- Addition of Summary of Protocol Amendments into the appendices.
- Correction of minor typographical errors (not individually listed).

This Protocol Amendment is considered **substantial**.

1 INTRODUCTION

This document details the statistical analysis of the data that will be performed for the Immodulon Therapeutics Limited study: IMM-101-015 - A study of the Safety and Efficacy of IMM-101 in Combination with Checkpoint Inhibitor in Patients with Advanced Melanoma.

The proposed analysis is based on the contents of Version 2 of the protocol (dated 16 December 2019). In the event of future amendments to the protocol, this statistical analysis plan (SAP) may be modified to account for changes relevant to the statistical analysis.

The table, listing and figure shells are supplied in a separate document which is approved separately.

2 STUDY OBJECTIVES AND DESIGN

2.1 Study Objectives

The primary objectives of this study are to investigate the effectiveness of IMM-101 combined with nivolumab in controlling advanced melanoma and to assess and describe the safety profile of the combination after a maximum of 18 months of treatment with IMM-101 + nivolumab. The safety and efficacy of the combination will be assessed in patients who are either previously untreated (cohort A), or whose disease has progressed during PD-1 blockade (cohort B) and compared with published data on the efficacy and adverse event (AE) profile of nivolumab alone.

2.1.1 Primary Objectives

The primary objectives of the study are:

- To evaluate Overall Response Rate (ORR) after a maximum of 18 months treatment, in patients with advanced melanoma receiving IMM-101 + nivolumab. ORR in both previously untreated patients (cohort A) and in patients whose disease has progressed during PD-1 blockade (cohort B) will be evaluated using Response Evaluation Criteria in Solid Tumours ([RECIST 1.1](#)¹). ORR will also be assessed for subgroups based on PD-L1 status (positive or negative/undetermined) in cohort A patients.
- To evaluate the safety and tolerability of the combination of IMM 101 + nivolumab in patients with advanced melanoma by examining the profile of AEs experienced.

2.1.2 Secondary Objectives

The secondary objectives of the study are:

- To evaluate Progression-free Survival (PFS) after a maximum of 18 months treatment in patients with advanced melanoma receiving IMM-101 + nivolumab for both cohort A and cohort B, assessed by RECIST 1.1.
- To evaluate Overall Survival (OS) and OS at 1 year in patients with advanced melanoma for both cohort A and cohort B.
- To evaluate changes in laboratory parameters.

- To evaluate local tolerability (injection site reactions).

2.1.3 Exploratory Objectives

The exploratory objectives of the study are:

- To evaluate the ORR in patients with advanced melanoma receiving IMM-101 + nivolumab using immune-related Response Criteria (irRC) for both cohort A and cohort B.
- To evaluate the Duration of Response and Time to Response in patients with advanced melanoma receiving IMM-101 + nivolumab for both cohort A and cohort B, assessed by RECIST 1.1.
- To evaluate Disease Control for patients in cohort B of the study only, defined as those patients with a response of stable disease (SD) based on RECIST 1.1. and assessed at each scan assessment point from Week 14 onwards.
- To evaluate Best Overall Response (BOR) for patients in cohort B to include any responses obtained following a change in therapy from IMM-101 + nivolumab to IMM-101 + ipilimumab, by including all tumour assessments on study.
- To evaluate the safety and tolerability of the combination of IMM 101 + ipilimumab in patients with advanced melanoma by examining the profile of AEs experienced for any patients in cohort B of the study who took IMM-101 + ipilimumab as subsequent treatment.
- Monitoring of selected markers of tumour burden and immunological status in patients receiving IMM-101 (to be reported separately to other endpoints).

2.2 Study Endpoints

2.2.1 Primary Endpoints

The primary efficacy endpoint of the study is the ORR calculated from the BOR of patients as assessed by RECIST 1.1. ORR will be assessed at the end of study or when all patients have withdrawn, if this is sooner. For cohort B, ORR will apply to BOR from tumour assessments during IMM-101 + nivolumab treatment only. ORR and BOR will also be assessed for subgroups based on PD-L1 status (positive or negative/undetermined) in cohort A patients.

The primary safety endpoint of the study is the incidence, frequency and severity of AEs, serious adverse events (SAEs), treatment related AEs, immune-related AEs, Grade 3 and above AEs and AEs leading to IMM-101 discontinuation or study withdrawal experienced during treatment with IMM-101 + nivolumab for both cohorts.

2.2.2 Secondary Endpoints

The secondary efficacy endpoints of the study are:

- PFS assessed by RECIST 1.1 after a maximum of 18 months treatment in patients receiving IMM-101 + nivolumab.
- OS and OS at 1 year, for both cohort A and cohort B. The median OS (if applicable) and OS rate at 12 months will be estimated.

The secondary safety endpoints of the study are:

- Incidence and frequency of laboratory parameter abnormalities.
- Change from baseline values in laboratory parameter values.
- Incidence and frequency of local injection site reactions.

2.2.3 Exploratory Endpoints

The exploratory efficacy endpoints of the study are:

- ORR using irRC in patients in both cohort A and cohort B receiving IMM-101 + nivolumab.
- Duration of Response and Time to Response for both cohort A and cohort B receiving IMM-101 + nivolumab and assessed by RECIST 1.1.
- Disease Control, for patients in cohort B of the study only and defined as those patients with a response of stable disease based on RECIST 1.1, assessed at each scan assessment point from Week 14 onwards.
- BOR for cohort B to include any responses obtained following a change in therapy from IMM-101 + nivolumab to IMM-101 + ipilimumab.
- Immunological markers from blood and biopsy samples (to be reported separately to other endpoints).

The exploratory safety endpoint of the study is for any patients in cohort B of the study who took IMM-101 + ipilimumab as subsequent treatment. The incidence, frequency and severity of AEs, SAEs, treatment related AEs, and immune-related AEs from the start of treatment with ipilimumab will be examined.

2.3 Study Design

This open-label, non-comparative, non-randomised study consists of two cohorts; patients with unresectable, Stage III or Stage IV metastatic melanoma who are either previously untreated (cohort A), or whose disease has progressed during PD-1 blockade (cohort B).

Treatment for patients in both cohorts is continued until disease progression (as assessed by RECIST 1.1) subject to the following qualifications: unacceptable side-effects, the Investigator's decision to discontinue treatment, withdrawal of patient consent, or 18 months of study treatment, whichever is the sooner. Patients with a complete response maintained over 2 scans should continue treatment unless the Investigator considered this not in the patient's best interest.

The study will continue until all patients have had the opportunity of 18 months treatment on study. Patients will be recruited from two sites within the UK.

2.4 Visit Structure

The visit structure and scheduled assessments are detailed in Section 8 and Appendix 1 of the protocol.

3 SAMPLE SIZE

Sufficient patients will be screened for 18 patients to be enrolled into cohort A and 8 into cohort B of this open-label study. Patients withdrawn during the course of the

study will not be replaced. No formal sample size calculation has been performed and the sample size is considered a sufficient and adequate number of patients to investigate the efficacy signals of IMM-101 combined with nivolumab in controlling advanced melanoma and to explore the safety profile of the combination therapy.

4 INTERIM DATA REVIEWS

By-cohort interim data reviews will be conducted for the primary efficacy and primary safety endpoints of ORR (RECIST 1.1) and incidence, frequency and severity of AEs, when all subjects have had the opportunity for 1 year on study (Cohort A) or after 6 months on study (Cohort B). No other endpoints will be presented at the interim analysis time points. All summaries will be presented on the Intent-to-Treat set with the exception of AEs which will be summarised using the Safety Analysis Set. These two analysis sets are expected to be the same as detailed in Section 5.3. The interim data reviews will be performed separately for each cohort and therefore the tables and listings will present only data for the relevant cohort. In tables the alternative cohort and if applicable, the overall column will be present but will not contain results data for the alternative cohort.

Due to the COVID-19 pandemic, recruitment was suspended at both study sites in March 2020. As the majority of Cohort A and B subjects had already been enrolled, the interim data review of background and demographic characteristics and of ORR will include only those subjects recruited to the point of recruitment suspension which will be 11 subjects in Cohort A and 5 subjects in Cohort B. The interim data review of background and demographic characteristics (see Section 4.1) and safety will include all subjects enrolled at the time of the data reviews, which may be more than these subjects if recruitment resumes prior to interim database lock for either interim data review. The listings of background and demographic characteristics will contain a flag to indicate subjects who did not have the opportunity to complete the 12 months and 6 months on study for Cohorts A and B respectively.

The tables and listings to be presented at each of the interim data reviews will be detailed in IMM-101-015 (ICS17002) Interim Analysis Outputs.pdf. The document also indicates the analysis set used to present each interim data review output, as this may differ from the analysis set used at the final analysis detailed in Table 1 of Section 5.3. An asterisk has also been added to the titles of the outputs which will be presented at interim data review in the shells document.

4.1 Background and Demographic Characteristics

Summary tables and listings will be provided for demography, baseline disease status, melanoma diagnosis details and previous systemic treatment for melanoma for the subjects included in the interim data reviews. Further information on each of these presentations can be found in Section 5.7 of this SAP.

4.2 Overall Response Rate

ORR (RECIST 1.1) will be assessed at the interim data review, using scan assessment results up to and including the 12-month assessment for the first 11 enrolled Cohort A subjects and for the first 5 Cohort B subjects up to and including the 6-month assessment. The scan assessments included for each interim data review are derived using dates for each subject. For example, for Cohort B, Week 26 is the 6-month

timepoint, hence scheduled scans up to Week 22 scan and any unscheduled scans up to Week 26 will be used according to date calculations. Week 30 scans will not be included. The 6-month timepoint will be calculated as 6 months from the date of first dosing with IMM-101 (Day 0). Similarly, with respect to the 12 month timepoint for Cohort A.

ORR is defined as the number of subjects with a BOR of CR or PR divided by the number of subjects in the Intent-to-treat analysis set in each cohort of the study. The BOR will be determined once all the data up to and including the 12-month assessments for Cohort A or the 6-month assessment for Cohort B are available. It is defined as the best response designation based on confirmed responses determined by the investigator according to RECIST 1.1, recorded between the date of first post-screening scan and the date of last scan at/prior to the assessment at the 12-month assessment (Cohort A) and 6-month assessment/last assessment prior to change of treatment to IMM-101 + ipilimumab whichever is sooner (Cohort B).

A summary table will be presented for the Objective Response Rate (RECIST 1.1) at last on-study assessment with data cut-off as defined above. Corresponding baseline and follow-up lesions assessments, response assessments and best objective response up to these time points will also be listed.

Further information on the derivation of BOR can be found in Section 5.13.1 of this SAP.

4.3 Adverse Events

Incidence, frequency and severity of AEs will be assessed at the interim data reviews, using all available AE information in the database up to the cut-off dates in each respective Cohort for all subjects.

4.4 Clinical Laboratory Evaluation

Summaries of the clinical significance over time for both haematology and biochemistry will be assessed at the interim data reviews, using all available information in the database up to the cut-off dates in each respective Cohort for all subjects.

5 ANALYSIS PLAN

5.1 General

Summary statistics for continuous variables will consist of the number of non-missing observations (n), mean, standard deviation (StD), minimum, median and maximum, unless specified otherwise.

For categorical variables the number and percentage of subjects in each category will be presented, based on the number of non-missing observations apart from disposition of subjects, protocol deviations, background and demographic characteristics, prior and concomitant medications/procedures and adverse events where the percentage will be based on the number of subjects in the analysis set, or subgroup of the analysis set, with a missing category presented where applicable. Any exceptions to these are detailed within the table, listing and figure shells.

The mean and median will be displayed to 1 more decimal place than the original data values and the StD will be displayed to 2 more decimal places than the original data values. The minimum and maximum will be displayed to the same number of decimal places as the original data. Percentages will be displayed to 0 decimal places; percentages will not be presented when the count is zero.

5.2 General Derivations

This section provides details of general derivations. Derivations specific to the parameter of interest are detailed within the specific SAP section.

5.2.1 Definition of Baseline

Baseline is defined as the last assessment value prior to first administration of IMM-101.

5.2.2 Visit and Study Day

Throughout this SAP any references to “Visit XX” refer to the pre-specified visits defined in the protocol where Day 0 (Visit 1 – Week 0) is the date of first administration of IMM-101.

Data listings by visit will additionally present study day, indicating the duration of time since first administration of IMM-101. Study day will be calculated relative to the first date of administration of IMM-101 (Study Day 1).

5.2.3 Incomplete Dates

For calculation purposes, incomplete dates will be completed using worst case. Further details are detailed in the relevant sections as required.

5.2.4 Scheduled Scan Windows

Each scan, whether scheduled or unscheduled, will be allocated to a scheduled scan time point if it is within the scheduled scan timetable window +/- 7 days (see protocol Appendix 1). If there is more than one scan within a scheduled scan time window, the closest scan prior to the scheduled timepoint, or after it if there are no scans prior, will be considered the scheduled scan for that timepoint. For efficacy assessments, all scans will be included whether they are scheduled or unscheduled. Listings of scan data will include the allocated visit (as defined above) and a flag to indicate if this differs from the original visit recorded at site.

5.2.5 Non-numeric Values

In the case where a variable is recorded as “>x”, “≥x”, “” or “≤x”, then for analysis purposes a value of x will be taken. Where a range of values is quoted the midpoint of the range will be taken. If a laboratory safety parameter is reported as being below the limit of quantification or < x, the value of the limit will be used in the calculation of summary statistics. The recorded value will be reported in listings.

5.2.6 Methods for Handling Withdrawals and Missing Data

In general, no imputations will be applied. Where imputation may be deemed appropriate, information is detailed in the analysis descriptions.

5.2.7 Site Pooling

Due to the small number of subjects, sites will be pooled for all summaries and analyses.

5.2.8 Subgroup Presentation

The following subgroups are of interest for presentation:

- PD-L1 status at screening (positive/negative or indeterminate) for Cohort A only.
- IMM-101 + ipilimumab in combination for Cohort B only.
- LDH at baseline (\leq upper limit of normal/ $>$ upper limit of normal).
- BRAF status at screening (wild type/mutant).
- M staging at screening (M1c and M1d combined/M0, M1a and M1b combined).

Subgroups will be presented provided the following criteria are met:

- For Cohort A the subgroup size is at least 33% of the enrolled Cohort A subjects and less than the total size of the ITT set in Cohort A.
- For Cohort B the subgroup size is at least 50% of the enrolled Cohort B subjects and less than the total size of the ITT set in Cohort B.

Where subgroups do not meet these criteria, information will be gathered from listings only and no summary tables will be provided for the clinical study report (CSR).

The use of these subgroups will be detailed in the relevant sections.

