### 11.7.2 Subgroups For Analysis

Subgroups of patients in both cohorts will be defined based on BRAF status (Wild type, Mutant), Disease stage (M staging:- M1c (if Cohort B, combined with M1d), M0 combined with M1a and M1b) and LDH at baseline ( $\leq$  ULN, > ULN categorisation). Subgroups of patients in cohort A will be defined based on PD-L1 status (PD-L1 positive and PD-L1 negative/indeterminate) at Screening. These subgroups will be summarised for the primary endpoint of ORR (RECIST 1.1) at the end of the study.

A subgroup of patients in cohort B will be defined as those cohort B patients who receive IMM-101 + ipilimumab as subsequent treatment (Cohort B IMM-101 + ipilimumab subgroup). This subgroup will be assessed for the primary safety endpoints of the incidence and frequency of adverse events, serious adverse events, treatment-related adverse events and immune-related adverse events (as listed in the SmPC for ipilimumab) experienced following the start of ipilimumab treatment up to the end of the study.

All subgroups will be summarised provided the respective subgroup size is at least 33% of the total size of the ITT set for cohort A and in cohort B, if at least 50% of the cohort B subjects are in the respective subgroup.

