Listings of the baseline and follow-up target lesions will be provided. These listings will be presented for both assessment using RECIST 1.1 and repeated for assessment using irRC. The response assessment for both RECIST 1.1 and irRC will also be listed. Listings of non-target lesions at baseline and follow-up will be presented. New lesions found after baseline will be listed and the assessments of these previously reported new lesions will also be listed.

A BOR listing will present the responses derived using RECIST 1.1 including confirmed responses only, unconfirmed responses, all responses (confirmed or unconfirmed) up until progression, confirmed responses at interim assessment, and all responses (confirmed or unconfirmed) including those after a treatment change in Cohort B. The BOR derived using irRC will also be presented.

Sensitivity Analysis

Two sensitivity analyses will be performed for comparability with published data:

1. The summary table will be repeated with BOR assessed using confirmed or unconfirmed responses.
2. The summary table will be repeated with BOR assessed using confirmed or unconfirmed responses up until disease progression (i.e. excluding any PR and CR responses following a PD response).

Unconfirmed responses do not need to follow Table 3 of RECIST 1.1. Instead, the BOR is defined as the best overall response during the defined period and does not need to be confirmed at a subsequent timepoint, hence overall responses whether confirmed or not are assessed in the evaluation of BOR.

Exploratory Analysis

Further summaries by subgroup will be provided where BOR is assessed using unconfirmed responses.

The summary table described above will be repeated for each of the following subgroups:

- PD-L1 status at screening (positive/negative or indeterminate) for Cohort A only.
- M staging at screening (M1c and M1d/M0, M1a and M1b) for Cohort A only.
- BRAF status at screening (wild type/mutant) for Cohort A only.
- LDH at baseline (\leq upper limit of normal/ $>$ upper limit of normal) for Cohort A and B.

The criteria for presentation of these outputs are described in Section 5.2.8.

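### The subgroup size rule has no exemption for PD-L1 in Cohort A, so the smaller PD-L1 group may get no tabulated ORR or exact CI although this estimate is part of the primary objective

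*SAP*

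**What the plan says.** The PD-L1 comparison appears at the top of the plan. SAP 2.1.1, under the primary objectives, states: "ORR will also be assessed for subgroups based on PD-L1 status (positive or negative/undetermined) in cohort A patients". Protocol 4.1 has the same sentence. SAP 2.2.1 repeats it under the primary endpoint and adds BOR: "ORR and BOR will also be assessed for subgroups based on PD-L1 status (positive or negative/undetermined) in cohort A patients". Protocol 5.1 describes relating efficacy to PD-L1 status as a need of the study, and every Cohort A patient must supply tissue adequate for the assay.

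SAP 5.2.8 lists PD-L1 status among the subgroups under one presentation rule. The lower limit in Cohort A is "For Cohort A the subgroup size is at least 33% of the enrolled Cohort A subjects", and the subgroup must also be "less than the total size of the ITT set in Cohort A". In Cohort B the lower limit is "For Cohort B the subgroup size is at least 50% of the enrolled Cohort B subjects". A subgroup that fails is covered by listings only and gets no summary table in the study report.

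SAP 5.13.1 places the PD-L1 table under exploratory analysis, together with M staging, BRAF and LDH, and closes the list with "The criteria for presentation of these outputs are described in Section 5.2.8". PD-L1 is not excepted.

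The limits come from protocol 11.7.2, which summarises subgroups "provided the respective subgroup size is at least 33% of the total size of the ITT set for cohort A" and uses 50% in Cohort B. SAP section 6, item 5, restates them with the added upper limit.

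**The concern.** Two parts of the plan pull against each other. One names ORR by PD-L1 group as something the study will assess as part of its primary objective. The other makes the table for each group depend on how many patients fall into it. If one group holds fewer than a third of the cohort, the report shows an ORR and exact interval for the larger group and none for the smaller. The objective would then be met for one of its two named groups, and nothing in the plan says this was intended.

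The same rule produces a lopsided display for other two-level factors. With a 50% limit in Cohort B, usually only the majority level of LDH qualifies, so a reader sees one level without its complement.

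**Working it through.** The plan states no sample size calculation, power or error rate, so it has no figure to reproduce. The check applies the rule to every possible split.

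**Inputs**
- Planned size: 18 in Cohort A and 8 in Cohort B (SAP section 3).
- Limits: 33% and 50% of enrolled subjects, and below the ITT size (SAP 5.2.8).
- PD-L1 has two levels: positive, and negative or indeterminate.
- Base case: every enrolled patient is dosed, so enrolled equals ITT.
- I read the rule as applying to each level separately.
- PD-L1-positive prevalence is not given in the documents. I assume 20% to 50%.

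**Cohort A threshold.** 0.33 × 18 = 5.94, so a group needs at least 6 patients. With k positive, the other group has 18 − k. Both reach 6 only for k = 6 to 12. For k = 1 to 5 or 13 to 17, one group is tabulated. For k = 0 or 18, neither is, because the only group then equals the whole ITT set.

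**Probability.** With prevalence p:

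P(both tabulated) = Σ (k = 6 to 12) C(18, k) p^k (1 − p)^(18 − k)

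P(at least one not tabulated) = 1 − P(both)

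P(neither) = p^18 + (1 − p)^18

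| Assumed p | Both tabulated | At least one not tabulated | Neither tabulated |
|---|---|---|---|
| 50% | 0.9037 | 10% | <0.01% |
| 40% | 0.7855 | 21% | 0.01% |
| 35% | 0.6436 | 36% | 0.04% |
| 30% | 0.4654 | 53% | 0.16% |
| 20% | 0.1329 | 87% | 1.8% |

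Almost all of the third column is the loss of exactly one group.

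**Sensitivity to the denominator.** SAP 5.2.8 counts against enrolled subjects, and the Enrolled Set (SAP 5.3) can include patients who were never dosed. Protocol 11.7.2 uses the ITT set for Cohort A. With 19 or 20 enrolled and 18 dosed, the limit is 6.27 or 6.60, so 7 are needed and both groups appear only for 7 to 11 positives.

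**Cohort B, LDH.** 0.50 × 8 = 4, so both levels qualify only at 4/4. P(4 of 8) is largest at p = 0.5: C(8, 4) × 0.5^8 = 70/256 = 27%. At p = 0.2 it is 5%.

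**The case against.** The strongest reply is that little information is lost. The overall Cohort A ORR with its exact interval is always tabulated. PD-L1 group sizes appear in the baseline disease summary (SAP 5.7.3). The first sensitivity table in SAP 5.13.1 uses confirmed or unconfirmed responses, as the subgroup tables do. If the larger group is tabulated, the smaller group's responders and denominator follow by subtraction, and patient-level BOR and PD-L1 results are listed. This stands. A reader might infer that the primary objective would go unreported, but the documents do not support that. What is missing is the planned ORR and exact interval for one group.

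A reader might also infer that both PD-L1 groups could readily disappear. With enrolled equal to ITT, two complementary groups cannot both fall below 33%. Both drop out only if all patients share one status, when the table would duplicate the overall one. Otherwise enrolment would have to exceed dosing greatly: for a 9/9 split, 28 enrolled against 18 dosed, since 0.33 × 28 = 9.24.

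Third, the limits are pre-specified in the protocol and depend on a screening characteristic, not on response. They are neither a SAP departure nor outcome-driven selection. A minimum group size is also a reasonable guard against over-reading: 2 responders of 5 has an exact 95% interval of about 5% to 85%. That explains the rule for incidental subgroups. It carries less weight for one named in the primary objective of a purely descriptive study, where the interval itself shows the imprecision.

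Finally, the 11 Cohort A patients recruited before the suspension might be taken as the relevant size. SAP section 4 uses that number for the interim review, whereas PD-L1 subgroups are assessed at the end of the study and planned enrolment remains 18.

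**Conclusion.** The conflict is real and limited in extent. Followed as written, the size rule can leave one named part of the primary objective without its tabulated ORR and exact interval. At 18 patients with enrolled equal to ITT, the chance is about 10% if half of patients are PD-L1 positive, 53% at 30% and 87% at 20%. The range rests wholly on assumed prevalence, and nothing in the documents narrows it. Even the most favourable value in the assumed range leaves about one chance in ten.

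The conflict starts in protocol 11.7.2 and is carried into the SAP. It concerns presentation: no data are lost and no bias in the response rate is implied.

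The Cohort B point is secondary. LDH is an exploratory subgroup that no objective names, and the missing level can be recovered by subtraction.

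**What to change.** In SAP 5.2.8, state that the size criteria do not apply to PD-L1 status in Cohort A. In 5.13.1, state that responders, denominator and exact 95% CI will be shown for both PD-L1 groups whatever their size. Every split from 1/17 to 17/1 is then tabulated, instead of only 6/12 to 12/6. Record the change from protocol 11.7.2 in SAP section 6; protocol 11.6 allows documentation in the final SAP.

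For the other two-level factors, apply the rule to the factor: both levels or neither. In Cohort B this leaves LDH to listings unless the split is 4/4, which is acceptable for a factor outside the objectives. Leave the IMM-101 + ipilimumab subgroup summaries as they are: that is a single group, and its safety summary is planned in SAP 5.15.1.

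The cost is a few lines of SAP text and one small table. The drawback is wide intervals for small groups, which the exact CI makes plain.
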